The PK assessment in rats showed that the dose correlated well with  $C_{max}$  and AUC. The major metabolites were glucuronide conjugate and sulfate conjugate, which were excreted in the urine. The urinary excretion of the unchanged drug was approximately 1% of the dose. Regarding the sulfate conjugate and glucuronide conjugate, neither a radical scavenging effect nor a lipid peroxidation inhibitory effect have been observed.

In an *in vitro* assay using human kidney homogenates, after deconjugation of the sulfate conjugate, the product was reconjugated with glucuronic acid and excreted mainly as the glucuronide conjugate in the urine. The glucuronidation reaction involved multiple uridine diphosphate glucuronyl transferases (UGTs), including UGT1A9. The effects of edaravone and its metabolites in inhibiting CYPs, UGTs, and transporters and inducing CYPs were not clinically significant. Edaravone was bound to human serum proteins at a rate of 91% to 92% (primarily to albumin).

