### 1.3.2 Clinical Study Results

The clinical study results of Radicut® (non-proprietary name: edaravone) injection are presented below.

Thus far, the following clinical studies have been performed: 5 clinical pharmacology studies in healthy adult subjects in Japan and Europe; 8 clinical studies in acute cerebral infarction patients in Japan, Europe, and South Korea, 3 clinical studies 3 in subarachnoid hemorrhage patients in Japan; and, 5 clinical studies in ALS patients in Japan.

In the clinical pharmacology study, Japanese healthy adult male subjects were given a single dose (0.2–2.0 mg/kg) or multiple doses (1.0 mg/kg/day for 7 days) of IV infusion over a period of 40 minutes or 3 hours to assess safety and the PK profile. After the single dose,

abnormal laboratory changes were observed in 2 subjects; however, values had returned to within the normal range at the end-of-study assessment, indicating no safety concerns. The highest levels of exposure to the unchanged drug in plasma were 3,061 ng/mL for  $C_{max}$  (1.5 mg/kg) and 3,005 ng•hr/mL for  $AUC_{0-24hr}$  (1.5 mg/kg). The  $C_{max}$  and  $AUC_{0-24hr}$  showed a proportional increase with dose. The elimination half-life and urinary excretion were nearly stable, regardless of the dose. No particular changes were observed in the PK profile after the single and multiple doses.

In the clinical pharmacology study outside Japan, Caucasian healthy adult male and female subjects were given rapid IV edaravone injection (0.05–0.2 mg/kg) followed by 24-hour continuous IV infusion (0.125–0.5 mg/kg/hr) to assess safety and the PK profile. The commonly observed AEs were infusion site pain, diarrhoea, and headache; however, they were also seen in the placebo group, and resolved prior to the end of the observation. The highest dose group (0.2 mg/kg + 0.50 mg/kg/hr) displayed a plasma unchanged drug exposure of 1,164.7 ng/mL for  $C_{max}$  and 22,455.6 ng•hr/mL for  $AUC_{0-24hr}$ .

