##### (1) Part 1 (single-dose study)

A single oral dose of the study drug will be given to subjects under fasting conditions in the morning or 30 minutes after breakfast. In Cohort S3-2, subjects in Cohort S3-1 will be given the same study drug that is allocated in Cohort S3-1 in a single oral dose after at least a 4-day washout period. Doses of Cohort S2 and thereafter are tentative. Based on the PK data obtained up to 24 hours post-dose and the safety data obtained up to 48 hours post-dose of the previous cohort, the sponsor and a medical expert will examine and determine the dose with the agreement of the investigator, such that the exposure of the minimum toxic dose (10,226 ng/mL for  $C_{max}$  and 1,226 ng•hr/mL for  $AUC_{0-24hr}$  in a free base form) is not exceeded. However, the highest dose in Part 1 shall not exceed 7,200 mg. The common ratio between the dose and the estimated mean  $C_{max}$  and  $AUC_{0-24hr}$  should be  $\leq 5$  between successive cohorts.

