**[Rationales for setting]**

Administration under fasting conditions was selected to avoid the effect of food on the PK parameters. Only at an estimated clinical dose of 800 mg, administration under fasted and fed conditions was established to examine the effect of food on the PK parameters.

The initial dose in the single-dose study was determined as described below. Based on the NOAEL of 10 mg/kg (through the IV route in rats) and 30 mg/kg (through the oral route in dogs), a human equivalent dose was calculated and divided by a safety factor of 10. As a result, the recommended maximum initial dose (at a body weight of 60 kg) was determined as 9.7 mg (through the IV route) and 100 mg (through the oral route). As the already approved IV dose is 60 mg per day, the initial oral dose was determined as 60 mg.

The highest dose was established not to exceed the exposure (10,226 ng/mL for  $C_{max}$  and 1,226 ng•hr/mL for  $AUC_{0-24hr}$  in a free base form) at the minimum toxic dose (30 mg/kg by the IV route) in rats that showed the highest sensitivity in the repeat-dose toxicity studies. The estimated  $AUC_{0-24hr}$  at the highest dose is as high as close to the  $AUC_{0-24hr}$  at the minimum toxic dose. Nevertheless, in a previous clinical study outside of Japan, an exposure of 1,886 ng•hr/mL for  $AUC_{0-24hr}$  (in a free base form) was observed in a subject receiving IV infusion, which exceeded the AUC at the minimum toxic dose. In that study, the commonly observed AEs were infusion site pain, diarrhoea, and headache, all of which were both reversible and also reported in the placebo group. Therefore, it was judged that the exposure raises no safety concerns.

The bioavailability (BA) of oral edaravone is estimated as 12%, based on the results of clinical studies of IV administration and an *in vitro* membrane permeability experiment. The highest possible dose was established as 7,200 mg, since if a dose  $\geq$ 7,200 mg were required as the highest dose, the calculated BA would be as low as <6%. In that case, it would be necessary to reconsider the development of this dosage form.

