The estimated PK parameters of oral edaravone in humans at the initial dose of 60 mg and the planned highest dose of 3,600 mg are as follows: 93 ng/mL for  $C_{max}$  and 202 ng•hr/mL for  $AUC_{0-24hr}$  at 60 mg (8 ng/mL for  $C_{max}$  and 16 ng•hr/mL for  $AUC_{0-24hr}$  in a free base form) and 5,577 ng/mL for  $C_{max}$  and 12,110 ng•hr/mL for  $AUC_{0-24hr}$  at 3,600 mg (452 ng/mL for  $C_{max}$  and 981 ng•hr/mL for  $AUC_{0-24hr}$  in a free base form).

Based on findings from the non-clinical studies, the estimated AEs are sedation, decreased blood pressure, and increased heart rate, which were transient in the studies. By observing the subjects' clinical symptoms and vital signs during the study period, it was determined to be feasible to conduct this study.

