#### **8.4 Judgment of Cohort Transition and Dose Change**

##### **(1) Part 1 (single-dose study)**

Upon finishing one cohort, the investigator will submit the "Results of Safety Evaluation up to 48 Hours Post-dose (During Hospitalization)" and "Investigator's View on Transition to the Next Cohort" to the sponsor in about 3 working days.

Based on the "Results of Safety Evaluation up to 48 Hours Post-dose (During Hospitalization)," "Investigator's View on Transition to the Next Cohort," and "Plasma Unchanged Drug Concentrations up to 24 Hours Post-dose\*," the sponsor will hold discussions with the medical expert, and obtain the "Medical Expert's View on Transition to the Next Cohort." Upon reaching a determination on whether or not to transit to the next cohort, along with the dose, the sponsor will prepare the "Notification of Transition to the Next Cohort and Dosing Regimen," and submit the form to the investigator with the "Plasma Unchanged Drug Concentrations up to 24 Hours Post-dose.\*" The investigator will inform the sponsor regarding whether or not he/she agrees with the above sponsor's

view using the "Cohort Transition Agreement Record," along with the reason if he/she disagrees. If the investigator's agreement is obtained, the sponsor will instruct to transit to the next cohort. If the investigator disagrees, the sponsor will hold discussions with the investigator until an agreement has been reached. Upon reaching an agreement, the sponsor will either instruct to transit to the next cohort with a determined dose or discontinue the study.

\*: The report includes a list of plasma unchanged drug concentrations,  $C_{max}$ , and AUC by subject.

(2) Part 2 (multiple-dose study)

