### **10.2 Pharmacokinetic Measurements**

The plasma drug concentrations of unchanged edaravone, sulfate conjugate, and glucuronide conjugate will be measured, and the following PK parameters will be calculated using a non-compartmental analysis.

(1) Plasma drug concentrations

Unchanged edaravone, sulfate conjugate, and glucuronide conjugate

(2) PK parameters

$AUC_{0-\text{last}}$ ,  $AUC_{0-12\text{hr}}$ ,  $AUC_{0-24\text{hr}}$ ,  $AUC_{0-\infty}$ ,  $C_{\text{max}}$ ,  $C_{\text{trough}}$ ,  $t_{\text{max}}$ ,  $t_{1/2}$ ,  $\lambda_z$ , MRT\*, CL/F\*,  $V_z/F^*$ , and  $V_{\text{ss}}/F^*$  (\*: calculated for unchanged edaravone only)

The laboratory that measures drug concentrations will prepare a plan for the measurements by the time the measurements are started, and prepare a report after completion of the measurements.

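### The Part 1 exposure ceiling is labelled as free base, but the protocol's own figures show it is unbound drug

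*Protocol*

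**What the plan says.** The dose-setting rule for Part 1 (Section 8.3.1 (1), repeated in Protocol Summary 5.2 (1)) requires that the minimum-toxic-dose exposure, Cmax 10,226 ng/mL and AUC0-24hr 1,226 ng•hr/mL, "in a free base form) is not exceeded". Footnote 4 of Table 1 relies on the same ceiling to allow a lower dose in Cohorts S5 and S6.

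The rationale in Section 8.3.1 uses the same label elsewhere:

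- Human predictions at 60 mg and 3,600 mg are given first without a label and then as free base, for example "in a free base form) and 5,577 ng/mL for" Cmax at 3,600 mg.
- The estimated AUC0-24hr "at the highest dose is as high as close to the" value at the minimum toxic dose.
- An AUC0-24hr of 1,886 ng•hr/mL, labelled free base, "was observed in a subject receiving IV infusion, which exceeded the AUC at the minimum toxic dose".

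On binding, Section 1.3.1 says "Edaravone was bound to human serum proteins at a rate of 91% to 92" percent. The drug is named only as edaravone powder (Section 7.1).

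On what the decision makers see, Section 8.4 (1) says: "The report includes a list of plasma unchanged drug concentrations", with Cmax and AUC by subject. On assays, Section 10.2 says: "The plasma drug concentrations of unchanged edaravone, sulfate conjugate, and glucuronide conjugate will be measured". It lists no unbound measurement.

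**The concern.** Free base describes a drug stripped of its salt. For a drug with no named salt, the natural reading is the measured parent compound, which is what the cohort-transition listing contains. If the ceiling is in fact protein-free drug, the number in the rule and the number in the report are on scales about 12-fold apart (1/0.081 = 12.3), and neither the rule nor Section 8.4 links them.

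The sponsor, the medical expert and the investigator all apply this threshold. Comparing the listing with 1,226 directly would halt escalation below the 800 mg that the protocol calls the estimated clinical dose. Cohort M2 is capped at two thirds of the highest Part 1 dose, so a mistaken stop would carry into Part 2.

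**Working it through.** **Inputs.** From the Section 8.3.1 rule: ceiling Cmax 10,226 ng/mL and AUC0-24hr 1,226 ng•hr/mL. From its rationale: predictions 93 and 202 (free base 8 and 16) at 60 mg, and 5,577 and 12,110 (free base 452 and 981) at 3,600 mg, each as Cmax and AUC0-24hr. From Section 1.3.1: 91% to 92% bound, so 8% to 9% unbound.

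**1. What factor links the two scales?** Ratio = labelled figure / unlabelled figure.

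- 3,600 mg: 452/5,577 = 0.0810; 981/12,110 = 0.0810.
- 60 mg: 8/93 = 0.086, with a rounding range of 7.5/93.5 = 0.080 to 8.5/92.5 = 0.092.
- 60 mg: 16/202 = 0.079, with a rounding range of 15.5/202.5 = 0.077 to 16.5/201.5 = 0.082.

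All four fit 0.081. Then 1 − 0.081 = 91.9% bound, inside the stated 91% to 92%. As a salt-to-base factor, 0.081 would need a salt 12.3 times the weight of the base, which is not plausible. The labelled predictions are therefore unbound drug.

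**2. Is the ceiling on that scale too?** It has no printed total-drug counterpart, so this is inferred.

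- The rationale says the top-dose AUC is close to the ceiling. As unbound, 981/1,226 = 0.80. As total, 12,110/1,226 = 9.9. Only the first is close.
- As total drug, the 800 mg prediction would be 12,110 × 800/3,600 = 2,691, or 2.2 times the ceiling.
- Section 1.3.2 gives AUC0-∞ 1,374 ng•hr/mL for the approved 60 mg infusion. Read as total drug, the ceiling would lie below exposure at the marketed dose.

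**3. Cross-check, approximate.** Section 1.3.2 says that the top dose group of the study outside Japan "displayed a plasma unchanged drug exposure of 1,164.7 ng/mL for" Cmax, with AUC0-24hr 22,455.6 ng•hr/mL. The rationale's 1,886 comes from a study outside Japan with the same commonly observed adverse events, presumably the same study. 1,886/22,455.6 = 0.084, inside 8% to 9%. One figure is a subject's and the other a group's, so this supports the scale but does not fix a factor. It also suggests that unchanged drug in plasma means total drug.

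**4. Dose at which AUC 1,226 is reached, on the protocol's linear prediction.**

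| Reading | Calculation | Dose |
|---|---|---|
| Total | 1,226 / (12,110/3,600) | 364 mg |
| Unbound, 0.081 | 1,226 / (981/3,600) | about 4,500 mg |
| Unbound, 8% | 1,226 / (0.08 × 12,110/3,600) | 4,556 mg |
| Unbound, 9% | 1,226 / (0.09 × 12,110/3,600) | 4,050 mg |

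All the unbound readings fall between the planned top dose of 3,600 mg and the 7,200 mg cap. On prediction, no planned cohort reaches the ceiling, and the ceiling would bind before the cap.

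**5. Headroom at 3,600 mg.** 12,110 × 0.08 = 969 (79% of 1,226); × 0.081 = 981 (80%); × 0.09 = 1,090 (89%).

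**6. Total-drug equivalents.**

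- AUC0-24hr: 1,226/0.08 = 15,325; /0.081 = 15,136; /0.09 = 13,622 ng•hr/mL.
- Cmax: 10,226/0.08 = 127,825; /0.09 = 113,622 ng/mL. The lower value is 113,622/5,577 = 20.4 times the 3,600 mg prediction, so Cmax does not bind.

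**The case against.** The case against giving this much weight has several parts.

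- **The misreading is unlikely and errs on the safe side.** Taken literally, the rule would put the marketed infusion and the planned 800 mg cohort above the toxic exposure, so the people who set the numbers would notice. The step ratio, the 7,200 mg cap and the stopping criteria do not depend on the label. All of this stands, and it keeps the point from being more serious. It does not make the printed label correct.
- **The scale can be recovered.** The rationale in Section 8.3.1 prints both scales side by side. That is true, but the Protocol Summary states the rule without those figures, and nobody should have to work out a threshold's units from its rationale.
- **A conversion may exist elsewhere.** The Procedures for Cohort Transition (Appendix 3) are not among the documents at hand and may contain one. The absence of an unbound assay shows little, because applying a fraction is a desk calculation. Both points stand. The finding is therefore that the rule is mislabelled and states no conversion where it is printed, not that none exists.
- **The 0.084 ratio is weak evidence.** Agreed. The conclusion rests on steps 1 and 2 of the working.
- **The headroom range comes from varying the fraction, not from the label.** Also true: the protocol's own pairs give 80%. The range shows only why the fraction should be written down.
- **A limit of 13,600 would be tighter than the one the protocol implies.** It is about 10% below 15,136. It is a cautious option for the sponsor, not part of the correction.

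**Conclusion.** The concern holds. The label on the Part 1 ceiling, and wherever else it appears in Section 8.3.1 and the Protocol Summary, is wrong: the figures are unbound drug. For the human predictions this follows directly from the paired values and the stated binding. For the ceiling it is a strong inference from the shared label and from the comparison with 981, because the total-drug reading would rule out the planned 800 mg dose.

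The two readings put the AUC limit at about 364 mg and about 4,500 mg. Those doses assume the protocol's linear prediction, and the second assumes a fraction of 0.081. The consequence of a literal reading is a needless stop, with no route shown to over-exposure. The correction should be made because this is an operative decision threshold, but it does not call the escalation design into question.

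**What to change.** - In Protocol Summary 5.2 (1), the Section 8.3.1 (1) rule and its rationale, replace the free-base wording with unbound (protein-free) drug.
- In the rule, state the unbound fraction used: 0.081 on the protocol's own figures, to be confirmed by the sponsor and aligned with the Procedures for Cohort Transition.
- Next to it, print the total-drug AUC0-24hr equivalent, so that the listing can be compared directly: about 15,100 ng•hr/mL at 0.081, or 13,600 to 15,300 over 9% to 8% unbound. If the sponsor prefers one cautious value, 13,600 is the lower end.
- A total-drug Cmax equivalent is optional, since it does not bind.

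The cost is a change of wording in those places and one added line, with no extra data, assay or visit. As a protocol change it needs the investigator's agreement and IRB approval under Section 15.

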**Table 1 Dose, Dosing Regimen, and Duration (Single-dose study [Part 1])**

Cohort	Dose	Condition of administration	Race	Duration	No. of subjects	
					Edaravone	Placebo
S1	60 mg	Fasting	Japanese	1 day	6	2
S2	240 mg 			1 day	6	2
S3-1	800 mg 			1 day	6	2
S3-2				1 day		
S4 	1,600 mg 			1 day	6	2
S5	2,400 mg 	Fasting	Caucasian	1 day	6	2
S6	3,600 mg 			1 day	6	2
S7 	800 mg 			1 day	6	2

1) Tentative doses are presented. The dose will be determined based on the PK and safety data collected up to the previous cohort.

2) For Cohort S4, polyvinyl alcohol and xanthan gum will be used as vehicles. Cohort S4 can be started using the same timing as Cohort S3-2.

- 3) The dose in Cohort S7 will be the same as that in Cohorts S3-1 and S3-2. Cohort S7 can be started at using same timing as Cohort S3-1.
- 4) A dose lower than in the previous cohort can be selected if it is judged that assessment of PK and safety at the maximum dosage not exceeding the exposure of the minimum toxic dose has been completed by the previous cohort.

**[Rationales for setting]**

Administration under fasting conditions was selected to avoid the effect of food on the PK parameters. Only at an estimated clinical dose of 800 mg, administration under fasted and fed conditions was established to examine the effect of food on the PK parameters.

The initial dose in the single-dose study was determined as described below. Based on the NOAEL of 10 mg/kg (through the IV route in rats) and 30 mg/kg (through the oral route in dogs), a human equivalent dose was calculated and divided by a safety factor of 10. As a result, the recommended maximum initial dose (at a body weight of 60 kg) was determined as 9.7 mg (through the IV route) and 100 mg (through the oral route). As the already approved IV dose is 60 mg per day, the initial oral dose was determined as 60 mg.

The highest dose was established not to exceed the exposure (10,226 ng/mL for  $C_{max}$  and 1,226 ng•hr/mL for  $AUC_{0-24hr}$  in a free base form) at the minimum toxic dose (30 mg/kg by the IV route) in rats that showed the highest sensitivity in the repeat-dose toxicity studies. The estimated  $AUC_{0-24hr}$  at the highest dose is as high as close to the  $AUC_{0-24hr}$  at the minimum toxic dose. Nevertheless, in a previous clinical study outside of Japan, an exposure of 1,886 ng•hr/mL for  $AUC_{0-24hr}$  (in a free base form) was observed in a subject receiving IV infusion, which exceeded the AUC at the minimum toxic dose. In that study, the commonly observed AEs were infusion site pain, diarrhoea, and headache, all of which were both reversible and also reported in the placebo group. Therefore, it was judged that the exposure raises no safety concerns.

The bioavailability (BA) of oral edaravone is estimated as 12%, based on the results of clinical studies of IV administration and an *in vitro* membrane permeability experiment. The highest possible dose was established as 7,200 mg, since if a dose  $\geq$ 7,200 mg were required as the highest dose, the calculated BA would be as low as <6%. In that case, it would be necessary to reconsider the development of this dosage form.

The estimated PK parameters of oral edaravone in humans at the initial dose of 60 mg and the planned highest dose of 3,600 mg are as follows: 93 ng/mL for  $C_{max}$  and 202 ng•hr/mL for  $AUC_{0-24hr}$  at 60 mg (8 ng/mL for  $C_{max}$  and 16 ng•hr/mL for  $AUC_{0-24hr}$  in a free base form) and 5,577 ng/mL for  $C_{max}$  and 12,110 ng•hr/mL for  $AUC_{0-24hr}$  at 3,600 mg (452 ng/mL for  $C_{max}$  and 981 ng•hr/mL for  $AUC_{0-24hr}$  in a free base form).

Based on findings from the non-clinical studies, the estimated AEs are sedation, decreased blood pressure, and increased heart rate, which were transient in the studies. By observing the subjects' clinical symptoms and vital signs during the study period, it was determined to be feasible to conduct this study.

**(2) Part 2 (multiple-dose study)**

A once-daily oral dose of the study drug will be given to subjects 30 minutes before breakfast. For twice-daily administration, an oral dose of the study drug will be given to subjects 30 minutes before breakfast and before bedtime (12 hours after the dose

before breakfast). (On Day 1 and Day X [day of the last dose], an oral dose of the study drug will be administered 30 minutes before breakfast only.) If effects of diet are predicted by oral administration 30 minutes before breakfast from the results of pharmacokinetics obtained in cohorts S3-1, S3-2 and M1, it is possible to change cohort M2 to oral administration 1 hour or 90 minutes before breakfast, or not to take breakfast after fasting administration only on the administration day.

The dose and duration for Cohorts M1 and M2, and the frequency of administration for Cohort M2 are tentative. Based on the PK and safety data collected in Part 1 and Cohort M1, the sponsor and the medical expert will examine and determine the actual value with the agreement of the investigator. The dose in Cohort M2 should be  $\leq 2/3$  of the highest dose in Part 1. The common ratio between the dose and the estimated mean  $C_{max}$  and  $AUC_{0-24hr}$  should be  $\leq 5$  between successive cohorts.

**Table 2 Dose, Dosing Regimen, and Duration (Multiple-dose study [Part 2])**

Cohort	Dose	Frequency of administration	Duration	No. of subjects	
				Edaravone	Placebo
M1	800 mg/day 	Once daily	5, 9, or 14 days 	6	3
M2	2,400 mg/day 	Once daily or twice daily 	5, 9, or 14 days 	6	3

- 1) The dose and duration for Cohorts M1 and M2, and the frequency of administration for Cohort M2 are tentative.
- 2) The dose and duration for Cohort M1 will be determined based on the PK and safety data collected up to Cohort S4.
- 3) The dose, frequency and duration for Cohort M2 will be determined based on the PK and safety data collected up to Cohorts S6 and M1.

#### [Rationales for setting]

In the multiple-dose study, an estimated clinical dose of 800 mg was established for Cohort M1. For Cohort M2, a dose between  $\leq 2/3$  of the highest dose in the single-dose study and a dose  $\geq 2$ -fold of that of Cohort M1 was established.

